### **9.3. Treatment of Missing and Spurious Data**

See general definitions in chapter 5.4.

### **9.4. Exclusion of Particular Information**

See general definitions in chapter 5.5.

No data are excluded from the specified analysis set and variables.

### **9.5. Descriptive Analyses**

For specification "Notes = descriptive", see general definitions in chapter 5.1.

### **9.6. Hypotheses & Statistical Tests**

There are no pre-defined statistical hypotheses.

## 10. ADE and DD Endpoints - Implantation

### CIP chapter 7.2.2. Endpoints

In this study the number of adverse device effects and device deficiencies (DD) that occur in patients, users or other persons will be evaluated ...

- Number of adverse device Effects / device deficiencies per number of implantations
- Number of adverse device Effects / device deficiencies and per number of follow-up cases

ADEs will be adjudicated by an internal adjudication board, whereby the seriousness and device relatedness will be re-examined. If any amply documented external physical influence (e.g. accident, general power blackout) or medical AE caused the ADE, it does not contribute to this endpoint.

ADEs and device deficiencies are adjudicated by an internal adjudication board.

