7.2.2 Endpoints

In this study the number of adverse device effects and device deficiencies (DD) that occur in patients, users or other persons will be evaluated. Definitions are given in section 18. The investigator is asked to report any ADEs or DD that occurred during implantations and follow-ups.

- Number of adverse device Effects / device deficiencies per number of implantations
- Number of adverse device Effects / device deficiencies and per number of follow-up cases

ADEs will be adjudicated by an internal adjudication board, whereby the seriousness and device relatedness will be re-examined. If any amply documented external physical influence (e.g. accident, general power blackout) or medical AE caused the ADE, it does not contribute to this endpoint.

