11.5 Pass/fail criteria

There are no pass/fail criteria. Any potential ADEs or DDs will be analyzed and discussed.

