### 10.2. Variables

#### Adjudicated Adverse Device Effects / Device Deficiencies

Data file, identifier record id	Notes	Variable name	Variable label	Variable Level	Nominal values
internal adjudication	Case listing for AETYP = AE	AETYP	Type of event	nominal	o AE o DD
		AESTDT	Onset date	date	n.a.
		PRUCASE	Related use case	nominal	o Implementation o PHD / Follow-up
		DEIDV	Related investigational device	nominal	o Renamic Neo programmer o ECG cable PK-222-L
		DIPRGSNR	Programmer serial number	text	n.a.
		DIECBID	ESG cable ID	nominal	01, 02, ..., 25
		AERELIDV	Adverse Event is related to the investigational device (device related ADE)	nominal	o Not related o Unlikely o Possible o Probable o Causal relationship
		AESER	Adverse Event is serious	nominal	o Yes o No
		AERELSET	Adverse Event is relevant for ADE/DD endpoint	nominal	o Yes o No
CORELSET	Please specify reason for No	text	n.a.		

 analysis set imp SAR = Yes and PRUCASE = Implementation

Data file, identifier record id	Notes	Variable name	Variable label	Variable Level	Nominal values
internal adjudication	Case listing for AETYP = DD	AETYP	Type of event	nominal	o AE o DD
		DERCDT	Date of detection	date	n.a.
		PRUCASE	Related use case	nominal	o Implementation o PHD / Follow-up
		DEIDV	Related investigational device	nominal	o Renamic Neo programmer o ECG cable PK-222-L
		DIPRGSNR	Programmer serial number	text	n.a.
		DIECBID	ESG cable ID	nominal	01, 02, ..., 25
		DEADED	Device efficiency is relevant for ADE/DD endpoint	nominal	o Yes o No
		COADED	Please specify reason for No	text	n.a.

Data file, identifier patient display id full	Notes	Variable name	Variable label	Variable Level	Nominal values
data SAR	descriptive	any ade SAR 	Any Adverse Device Effect (serious or non-serious) based on internal adjudication	nominal	o Yes o No
data SAR	descriptive	any sade SAR 	Any Serious Adverse Device Effect based on internal adjudication	nominal	o Yes o No
data SAR	descriptive	any dd SAR 	Any Device Deficiency	nominal	o Yes o No
data SAR	descriptive	any ade dd SAR 	Any Adverse Device Effect (serious or non-serious) or Device Deficiency based on internal adjudication	nominal	o Yes o No
data SAR	descriptive	n ade SAR 	Number of Adverse Device Effects (serious or non-serious) based on internal adjudication	metric to be reported as nominal	o 1 o 2 ...

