data SAR	descriptive	n sade SAR 	Number of any Serious Adverse Device Effects based on internal adjudication	metric to be reported as nominal	o 1 o 2 ...
data SAR	descriptive	n dd SAR 	Number of any Device Deficiencies based on internal adjudication	metric to be reported as nominal	o 1 o 2 ...
data SAR	descriptive	n ade dd SAR 	Number of any Adverse Device Effects (serious or non-serious) and Device Deficiencies based on internal adjudication	metric to be reported as nominal	o 1 o 2 ...

 If specific patient with AERELSET = Yes AND AESER = No  
 THEN any ade SAR = Yes  
 ELSE any ade SAR = No

 If specific patient with AERELSET = Yes AND AESER = Yes  
 THEN any sade SAR = Yes  
 ELSE any sade SAR = No

 If specific patient with DEADED = Yes  
 THEN any dd SAR = Yes  
 ELSE any dd SAR = No

 If specific patient with AERELSET = Yes OR DEADED = Yes  
 THEN any ade dd AERELSET SAR = Yes  
 ELSE any ade dd SAR = No

 Count number of events per patient with AERELSET = Yes AND AESER = No

 Count number of events per patient with AERELSET = Yes AND AESER = Yes

 Count number of events per patient with DEADED = Yes

 Count number of events per patient with AERELSET = Yes OR DEADED = Yes

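### SAP chapters 10 and 11 tabulate only those device deficiencies that the internal board marks as relevant, without criteria, whereas CIP 7.2.2 provides adjudication and exclusion for ADEs only

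*SAP*

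**What the plan says.** CIP 7.2.2 defines the endpoint: "the number of adverse device effects and device deficiencies (DD) that occur in patients, users or other persons will be evaluated". On adjudication it says "ADEs will be adjudicated by an internal adjudication board, whereby the seriousness and device relatedness will be re-examined". Its exclusion concerns external physical influences and other medical causes, and is worded for the same events: "or medical AE caused the ADE, it does not contribute to this endpoint". Neither sentence mentions DDs. CIP 11.5 adds "Any potential ADEs or DDs will be analyzed and discussed".

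SAP chapters 10 (implantation) and 11 (PHD and follow-up) reproduce the CIP text and then add a sentence of their own: "ADEs and device deficiencies are adjudicated by an internal adjudication board". SAP 10.2 gives the board a Yes/No field for each DD, DEADED, labelled "Device efficiency is relevant for ADE/DD endpoint" (evidently meaning deficiency), and a free-text field, COADED, for the reason when the answer is No.

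The derived variables use that field as a filter. The patient-level indicator `any dd` begins "If specific patient with DEADED = Yes" (footnote 18). The count `n dd` is "Count number of events per patient with DEADED = Yes" (footnote 22). The combined ADE/DD variables take their DD part from the same condition (footnotes 19 and 23). Chapter 11 repeats all of this.

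The case listing for DDs is conditioned on AETYP = DD and not on DEADED, so it shows both the board's decision and its reason.

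**The concern.** ADEs and DDs are the study's only endpoints, and few events are expected (CIP 5.3), so the handling of a single DD is visible in the result. The study is open and uncontrolled, the board is internal, and there is no data monitoring committee (CIP 18.11). In that setting the rule for counting an event should be fixed in advance and should match the CIP.

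Here the two documents differ on what is counted, and the SAP gives no rule for when a DD is not relevant. CIP 18.3 defines a DD broadly, including use errors and inadequate labelling. Without criteria, a use error could be set aside although it meets that definition. A reader of the summary table could then take a filtered rate for the CIP endpoint. The label of `any dd` makes this easier: unlike the other derived ADE and DD variables, it does not say that the result rests on internal adjudication.

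**Working it through.** **1. The two rules side by side.**

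| Item | CIP 7.2.2 | SAP 10–11 |
|---|---|---|
| Adjudicated | ADEs | ADEs and DDs |
| Exclusion from the endpoint | ADEs, for named causes | ADEs (AERELSET = No) and DDs (DEADED = No) |
| Criteria for excluding a DD | none, as no exclusion is provided | none stated; free-text reason only |
| DD count in tables | DDs that occur | DDs with DEADED = Yes |

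**2. Direction.** Within an analysis set and use case, tabulated DDs = listed DDs − DDs with DEADED = No. The tabulated number is thus at most the listed number, and equal to it if the board never answers No.

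**3. Size per event.** The planned denominators are 50 implantations (CIP 11.2.1) and 100 PHD or follow-up cases (CIP 11.2.2). One DD set aside lowers the number of DDs per case by 1/50 = 2.0 points or 1/100 = 1.0 point. The patient-level `any dd` moves by the same amount only if that was the patient's sole counted DD. As an illustration, 3/50 = 6.0% (exact 95% interval 1.25% to 16.55%) becomes 2/50 = 4.0% (0.49% to 13.71%). The SAP plans no such intervals; they only give scale.

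**4. The plan's own detection figures.** CIP 11.2 gives the chance of seeing at least one, two or three ADEs or DDs when a problem has 5% probability. The formula is P(X ≥ r) = 1 − Σ C(n,k) p^k (1−p)^(n−k), summed over k = 0 to r−1, with p = 0.05.

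- n = 50: 0.9231, 0.7206, 0.4595, against a stated 92%, 72%, 46%.
- n = 100: 0.9941, 0.9629, 0.8817, against a stated 99%, 96%, 88%.

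All six agree with the CIP. They assume that every such event is counted.

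**5. Sensitivity.** Let q be the share of all ADEs and DDs occurring at that 5% rate that the board sets to No. The documents give no value, so q is an assumption. Replace p by 0.05(1 − q); for r = 1, n = 50 and q = 0.20 this gives 1 − 0.96^50 = 0.8701.

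| q (assumed) | n = 50: ≥1 / ≥2 / ≥3 | n = 100: ≥1 / ≥2 / ≥3 |
|---|---|---|
| 0 | 0.9231 / 0.7206 / 0.4595 | 0.9941 / 0.9629 / 0.8817 |
| 0.10 | 0.9000 / 0.6643 / 0.3922 | 0.9900 / 0.9428 / 0.8328 |
| 0.20 | 0.8701 / 0.5995 / 0.3233 | 0.9831 / 0.9128 / 0.7679 |
| 0.30 | 0.8316 / 0.5262 / 0.2548 | 0.9716 / 0.8688 / 0.6841 |
| 0.50 | 0.7180 / 0.3565 / 0.1294 | 0.9205 / 0.7166 / 0.4578 |

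If only DDs are set aside, q is the share of DDs removed multiplied by the share of events that are DDs, so the effect is smaller. These figures concern the tables only; a reader of the listing still sees the events.

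**The case against.** The best reply is that nothing is concealed and little depends on the rate. The DD listing prints the board's decision, the reason, the use case and the programmer serial number. With few events, a reader can recover the unfiltered number by hand. Problems noticed by investigators are also tabulated by feature and accessory without adjudication (SAP 12, 13 and 15, repeated in 14 and 16), although these are not DD counts. The study has no hypothesis and no pass/fail criterion, and CIP 11.2 places its value in discussing the types and circumstances of events. The label complaint is small, because `any dd` stands under a sub-heading that says adjudicated.

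The CIP is also silent on adjudicating DDs; it does not forbid it. CIP 7.4 says that DDs are assessed under section 18 and the sponsor's SOPs, which are not available here and might contain criteria.

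All this limits the weight of the point, but the mismatch remains. A listing is not a pre-specified count of the endpoint. A general reference to SOPs does not provide for leaving DDs out of it.

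Two stronger readings are tempting, and the documents support neither. A reader might infer that the DD rates can only be biased downward. The filter does lower or preserve the count, but that is bias only if genuine DDs are removed. Setting aside a report that is not a deficiency of the investigational device would correct an overcount, and the documents show no removal of either kind. A reader might also infer that unadjudicated ADE rows are needed. CIP 7.2.2 expressly provides for adjudicating ADEs, so such rows would be a preference and would not repair a departure from the plan.

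**Conclusion.** The point stands in a limited form. The SAP extends adjudication and exclusion to DDs, which CIP 7.2.2 provides for ADEs only. It states no criteria and summarises only the DDs that pass. Followed as written, it can report a DD rate below the CIP endpoint by 2 points per DD set aside in 50 cases, or 1 point in 100. This assumes the planned numbers of cases and at least one answer of No. If the board never answers No, the two counts agree. How often it would do so cannot be judged from the documents. Because removals are listed with reasons and no decision rule uses the rate, this is a modest correction that is worth making, and it is not a threat to the study's conclusions.

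**What to change.** In SAP 10.2, and by repetition in chapter 11:

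- For `any dd`, `n dd` and the combined ADE/DD variables, add a row counting all DDs (AETYP = DD, whatever the value of DEADED), split by PRUCASE, and name it as the CIP 7.2.2 endpoint. In the combined variables the ADE part keeps its adjudicated definition.
- Show the DEADED = Yes row beside it as the adjudicated result.
- Build both rows from the adjudication dataset, since the SAP shows PRUCASE only there. Check the total against the `device deficiency` dataset, which SAP 5.9 lists for analysis but chapters 10 and 11 do not use.
- Limit DEADED = No to stated reasons, such as a report that does not meet the CIP 18.3 definition or does not concern the investigational device.
- Label the DEADED = Yes version of `any dd` as based on internal adjudication, as `n dd` already is, and correct the wording of the DEADED label.

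The cost is some SAP wording and a few extra table rows. The DD rate may look slightly less favourable than the adjudicated one.

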### 10.1. Analysis Set and Data Selection

All analyses are performed for patients in the implantation analysis set using a specific data selection before / at implantation.

### 10.2. Variables

#### Adjudicated Adverse Device Effects / Device Deficiencies

Data file, identifier record id	Notes	Variable name	Variable label	Variable Level	Nominal values
internal adjudication	Case listing for AETYP = AE	AETYP	Type of event	nominal	o AE o DD
		AESTDT	Onset date	date	n.a.
		PRUCASE	Related use case	nominal	o Implementation o PHD / Follow-up
		DEIDV	Related investigational device	nominal	o Renamic Neo programmer o ECG cable PK-222-L
		DIPRGSNR	Programmer serial number	text	n.a.
		DIECBID	ESG cable ID	nominal	01, 02, ..., 25
		AERELIDV	Adverse Event is related to the investigational device (device related ADE)	nominal	o Not related o Unlikely o Possible o Probable o Causal relationship
		AESER	Adverse Event is serious	nominal	o Yes o No
		AERELSET	Adverse Event is relevant for ADE/DD endpoint	nominal	o Yes o No
CORELSET	Please specify reason for No	text	n.a.		

 analysis set imp SAR = Yes and PRUCASE = Implementation

Data file, identifier record id	Notes	Variable name	Variable label	Variable Level	Nominal values
internal adjudication	Case listing for AETYP = DD	AETYP	Type of event	nominal	o AE o DD
		DERCDT	Date of detection	date	n.a.
		PRUCASE	Related use case	nominal	o Implementation o PHD / Follow-up
		DEIDV	Related investigational device	nominal	o Renamic Neo programmer o ECG cable PK-222-L
		DIPRGSNR	Programmer serial number	text	n.a.
		DIECBID	ESG cable ID	nominal	01, 02, ..., 25
		DEADED	Device efficiency is relevant for ADE/DD endpoint	nominal	o Yes o No
		COADED	Please specify reason for No	text	n.a.

Data file, identifier patient display id full	Notes	Variable name	Variable label	Variable Level	Nominal values
data SAR	descriptive	any ade SAR 	Any Adverse Device Effect (serious or non-serious) based on internal adjudication	nominal	o Yes o No
data SAR	descriptive	any sade SAR 	Any Serious Adverse Device Effect based on internal adjudication	nominal	o Yes o No
data SAR	descriptive	any dd SAR 	Any Device Deficiency	nominal	o Yes o No
data SAR	descriptive	any ade dd SAR 	Any Adverse Device Effect (serious or non-serious) or Device Deficiency based on internal adjudication	nominal	o Yes o No
data SAR	descriptive	n ade SAR 	Number of Adverse Device Effects (serious or non-serious) based on internal adjudication	metric to be reported as nominal	o 1 o 2 ...
data SAR	descriptive	n sade SAR 	Number of any Serious Adverse Device Effects based on internal adjudication	metric to be reported as nominal	o 1 o 2 ...
data SAR	descriptive	n dd SAR 	Number of any Device Deficiencies based on internal adjudication	metric to be reported as nominal	o 1 o 2 ...
data SAR	descriptive	n ade dd SAR 	Number of any Adverse Device Effects (serious or non-serious) and Device Deficiencies based on internal adjudication	metric to be reported as nominal	o 1 o 2 ...

 If specific patient with AERELSET = Yes AND AESER = No  
 THEN any ade SAR = Yes  
 ELSE any ade SAR = No

 If specific patient with AERELSET = Yes AND AESER = Yes  
 THEN any sade SAR = Yes  
 ELSE any sade SAR = No

 If specific patient with DEADED = Yes  
 THEN any dd SAR = Yes  
 ELSE any dd SAR = No

 If specific patient with AERELSET = Yes OR DEADED = Yes  
 THEN any ade dd AERELSET SAR = Yes  
 ELSE any ade dd SAR = No

 Count number of events per patient with AERELSET = Yes AND AESER = No

 Count number of events per patient with AERELSET = Yes AND AESER = Yes

 Count number of events per patient with DEADED = Yes

 Count number of events per patient with AERELSET = Yes OR DEADED = Yes

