18.5 Definition of serious adverse device effect

An ADE* that resulted in any of the consequences characteristic of a serious adverse event is considered serious.

*see ISO 14155 3.36

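### The two SAP rows labelled as all adverse device effects are coded to count only the non-serious ones

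*SAP*

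**What the plan says.** The variable table in SAP 10.2 defines a patient-level indicator and an event count for each of ADEs, serious ADEs, device deficiencies (DDs), and ADEs and DDs combined. The ADE indicator, `any ade SAR`, is labelled "Any Adverse Device Effect (serious or non-serious) based on internal adjudication". The ADE count, `n ade SAR`, is labelled "Number of Adverse Device Effects (serious or non-serious) based on internal adjudication".

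The footnotes give the code:

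- Footnote 16, for `any ade SAR`: "If specific patient with AERELSET = Yes AND AESER = No".
- Footnote 20, for `n ade SAR`: "Count number of events per patient with AERELSET = Yes AND AESER = No".
- Footnote 17, for `any sade SAR`: "If specific patient with AERELSET = Yes AND AESER = Yes". Footnote 21 uses the same condition for the count.
- Footnote 23, for `n ade dd SAR`: "Count number of events per patient with AERELSET = Yes OR DEADED = Yes".
- Footnote 19, for `any ade dd SAR`, has the same condition as footnote 23, but its assignment line reads "THEN any ade dd AERELSET SAR = Yes".

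In the same table AERELSET marks an adverse event as counting towards the endpoint, AESER marks it as serious, and DEADED marks a DD as counting towards the endpoint. SAP 11.1 repeats all chapter 10 analyses for the discharge and follow-up cases.

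Protocol 7.2.2 sets the endpoint as numbers of ADEs and DDs, with no limit on seriousness. Protocol 18.5 makes a serious ADE a kind of ADE: "An ADE* that resulted in any of the consequences characteristic of a serious adverse event is considered serious".

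**The concern.** The label and the code of the same variable contradict each other. The label covers all ADEs and the code covers only non-serious ones. A programmer has to break one of them, and the SAP does not say which governs. Nothing in SAP 10.3 to 10.6 or 11.1 overrides the footnotes.

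Followed literally, the code reports a subset (serious ADEs) as present while the set that contains it (any ADE) is absent in the same patient. The error runs one way only: the row that a reader takes as the ADE total omits the most severe events. ADEs and DDs are the only endpoints of a pre-market study meant to support regulatory approval.

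**Working it through.** **1. Conditions side by side**

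| Row | Label covers | Code counts |
|---|---|---|
| `any ade`, `n ade` (fn 16, 20) | serious and non-serious ADEs | AERELSET = Yes and AESER = No |
| `any sade`, `n sade` (fn 17, 21) | serious ADEs | AERELSET = Yes and AESER = Yes |
| `any dd`, `n dd` (fn 18, 22) | DDs | DEADED = Yes |
| `any ade dd`, `n ade dd` (fn 19, 23) | serious and non-serious ADEs, and DDs | AERELSET = Yes or DEADED = Yes |

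The combined rows have the same serious-or-non-serious wording in their labels and no AESER condition. The labels, protocol 7.2.2 and protocol 18.5 therefore agree with each other, and footnotes 16 and 20 are the odd ones out. The code as it stands is a split into non-serious ADEs, serious ADEs and DDs, with the first part labelled as the total.

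**2. Worked example (constructed data, 50 implantations)**

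Patient A has one serious ADE. B has one non-serious ADE. C has one of each. D has one DD. The other 46 have no event. All events count towards the endpoint. Event counts are summed over patients.

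| Row | As coded | As labelled |
|---|---|---|
| `n ade` | 2 (B, C) | 4 (A, B, C twice) |
| `n sade` | 2 (A, C) | 2 |
| `n dd` | 1 (D) | 1 |
| `n ade dd` | 5 | 5 |
| `any ade` | 2/50 = 4% | 3/50 = 6% |
| `any sade` | 2/50 = 4% | 2/50 = 4% |
| `any dd` | 1/50 = 2% | 1/50 = 2% |
| `any ade dd` (by its IF condition) | 4/50 = 8% | 4/50 = 8% |

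As coded, 2 + 2 + 1 = 5, the three-way split. With the labels honoured, ADEs plus DDs give 4 + 1 = 5, which agrees with footnote 23.

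Event totals can be rebuilt by adding `n ade` and `n sade`, if the reader knows the code. Patient totals cannot: 2 + 2 = 4, but 3 patients had an ADE, because C is in both rows. Subtracting `any dd` from `any ade dd` (4 − 1 = 3) works here only because no patient has both an ADE and a DD.

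**3. Effect on the chance that the any-ADE row is non-zero**

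The protocol's own planning figures come first. With 5% probability per case, the binomial chance of at least one, two or three events is 92.3%, 72.1% and 45.9% for n = 50, and 99.4%, 96.3% and 88.2% for n = 100. These match protocol 11.2.1 (92/72/46%) and 11.2.2 (99/96/88%). They refer to ADEs or DDs combined, so the coding error does not affect them.

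For illustration, take the whole 5% as ADEs, one per case, with a share *s* that is serious. The coded row is then non-zero with probability 1 − (1 − 0.05(1 − *s*))^n:

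| Serious share *s* | n = 50 | n = 100 |
|---|---|---|
| 0 (same as labelled) | 92.3% | 99.4% |
| 10% | 90.0% | 99.0% |
| 25% | 85.2% | 97.8% |
| 50% | 71.8% | 92.0% |

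The documents give no serious share, so these values of *s* are assumptions.

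**The case against.** The case for leaving this alone is that nothing is lost. Serious ADEs have their own rows, every adjudicated adverse event is listed with its seriousness and endpoint flags, and the combined count includes them. The endpoint bullets in protocol 7.2.2 can be read as one combined ADE/DD count. On that reading the endpoint rows are the combined ones, whose conditions are right, and only a component row is wrong. The protocol expects very few events (5.2, 5.3), and with no serious ADE the two rows are numerically correct. There is no hypothesis (7.2.1) and no pass/fail criterion (11.5). The probabilities in the last table describe one table row and not the study's ability to detect events.

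All of this stands, and it limits the weight of the point. It does not remove the contradiction. The number of patients with any ADE is in no summary row, and the combined patient-level row has its own naming slip in footnote 19.

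One caveat on the arithmetic is also fair. SAP 5.4 imputes no endpoint data. A record with AERELSET = Yes and AESER missing would enter footnote 23 but neither footnote 20 nor 21. The three-way sum, and the statement that the shortfall equals the number of serious ADEs, therefore assume that AESER is complete.

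**Conclusion.** The concern holds. As written, `any ade SAR` and `n ade SAR` contradict their labels, for implantations and for discharge/follow-up cases alike. With AESER complete, the event count is low by exactly the number of serious ADEs, and the patient count by the number of patients whose endpoint-relevant ADEs are all serious. If no serious ADE occurs, the error is zero.

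The example of 2 against 4 events, and 4% against 6% of patients, shows the mechanism and is not a forecast. The practical consequence is limited, because the serious events are reported elsewhere and no decision rule depends on the row. It should still be corrected, since it concerns the study's only endpoints.

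**What to change.** - **Footnotes 16 and 20:** delete the AESER = No condition, so that both variables count every event with AERELSET = Yes. If the non-serious subset is wanted, add it as a separately labelled variable.
- **Footnote 19 (erratum):** make the THEN branch assign the declared variable, `any ade dd SAR`.
- **Minor clarification:** protocol 18.3 sends a DD that caused an adverse event to the adverse event form, while 18.8.1 asks for a DD form for DDs in general. Reconcile the two, then label `any dd SAR` and `n dd SAR` to match what they contain.

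The cost is the wording of three footnotes, one or two labels and a few program lines, with no new data and no new patients. Protocol 11.8 allows the SAP to be updated before database freeze or closure. After that, the change would have to be declared as a deviation in the statistical and clinical reports.

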 IF analysis set enr SAR = Yes AND  
 any general assessments per patient with  
 ([PRSVPRG = Yes AND autom SVTYP = Pre-hospital discharge follow-up (PHD)] OR  
 [PRSVPRG = Yes AND autom SVTYP = Regular follow-up after PHD])  
 THEN analysis set FUP SAR = Yes  
 ELSE analysis set FUP SAR = No

Subgroups

Data file, identifier patient display id full & DIDVTYP	Variable name	Variable label	Variable level	Nominal values
device log details	helpvar device type	hidden technical field: Short name for General type of device	nominal	
 
○ CRT
 
○ CRT-P
 
○ ICD
 
○ ICM
 
○ IPG
 

Data file, identifier patient display id full	Variable name	Variable label	Variable level	Nominal values
data SAR	subgroup device type SAR 	Subgroup type of device	nominal	
 
○ CRT
 
○ CRT-P
 
○ ICD
 
○ ICM
 
○ IPG
 

 Patient-specific type of device data for helpvar device type not missing  
subgroup device type SAR = helpvar device type

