### 11.1. Analysis Set and Data Selection

All analyses are performed for patients in the PHD & follow-up analysis set using a specific data selection after implantation.

All analyses from chapter 10 ADE and DD Endpoints - Implantation are repeated for these data.

---

 analysis set PHD FUP SAR = Yes and PRUCASE = PHD / Follow-up

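### SAP footnote 19 writes Yes and No to two different variable names, so the per-patient flag for any ADE or device deficiency cannot become Yes if programmed as written

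*SAP*

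**What the plan says.** The endpoint table in SAP 10.2 declares `any ade dd SAR`, with values Yes and No, to be reported descriptively. Its label is "Any Adverse Device Effect (serious or non-serious) or Device Deficiency based on internal adjudication", and it points to footnote 19.

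Footnote 19 has three lines:
- condition: "If specific patient with AERELSET = Yes OR DEADED = Yes"
- if true: "THEN any ade dd AERELSET SAR = Yes"
- otherwise: "ELSE any ade dd SAR = No"

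Footnotes 16 to 18, which define the neighbouring flags, each use one name in both branches; footnote 18, for example, has "THEN any dd SAR = Yes" and sets the same variable to No otherwise. The companion count `n ade dd SAR` is defined in footnote 23: "Count number of events per patient with AERELSET = Yes OR DEADED = Yes".

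SAP 11.1 repeats all chapter 10 analyses for PHD and follow-up, selecting with "analysis set PHD FUP SAR = Yes and PRUCASE = PHD / Follow-up". The table in SAP 7.1 declares that set under the same name, but footnote 4, which derives it, reads "THEN analysis set FUP SAR = Yes" and uses that shorter name in its ELSE branch too.

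**The concern.** The flag that the table reports is not the one that footnote 19 sets to Yes. A patient with a relevant event has nothing written to `any ade dd SAR`; a patient without one gets No. Because SAP 5.1 takes relative frequencies over non-missing values, the affected patients disappear from numerator and denominator alike, and the percentage comes out as 0% whatever happened. The error can only favour the device.

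ADEs and DDs are the only endpoints of this pre-market study (CIP synopsis and 7.2.2), and the sample-size reasoning in CIP 11.2 is framed in terms of seeing ADEs or DDs. A composite flag that always shows 0% would be a misleading line in the chapter that regulators are likely to read first.

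**Working it through.** **Inputs.** The condition and assignments come from SAP footnote 19, the denominator rule from SAP 5.1, and the case numbers (50 implantations, 100 PHD or follow-up cases) and the 5% probability from CIP 11.2.1 and 11.2.2. The event counts used below are assumed for illustration; the documents give none.

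**The plan's own figures.** The probability of at least r events among n cases at p = 0.05 is the binomial upper tail; for r = 1 it is 1 − 0.95^n.

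| n | r ≥ 1 | r ≥ 2 | r ≥ 3 | CIP states |
|---|---|---|---|---|
| 50 | 92.31% | 72.06% | 45.95% | 92 / 72 / 46% |
| 100 | 99.41% | 96.29% | 88.17% | 99 / 96 / 88% |

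All six reproduce, and this point disputes none of them. They show how likely it is that the flag would matter: if a problem exists at the planning probability of 5%, there is a 92% chance that at least one of 50 implantation cases triggers the faulty branch.

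**Footnote 19 executed literally.** `AERELSET` and `DEADED` can each be Yes, No or missing, which gives nine combinations.
- In the 5 combinations where at least one is Yes, `any ade dd AERELSET SAR` is set to Yes and `any ade dd SAR` stays unassigned.
- In the other 4, `any ade dd SAR` is set to No.

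The reported flag is never Yes. With both branches writing to `any ade dd SAR`, it is Yes in the 5 and No in the 4, as the label requires.

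**Effect on the table.** With k of N patients having a relevant event, the rule as written gives 0/(N − k); the intended result is k/N.

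| N | k (assumed) | As written | Intended |
|---|---|---|---|
| 50 | 1 | 0/49 = 0.0% | 1/50 = 2.0% |
| 50 | 3 | 0/47 = 0.0% | 3/50 = 6.0% |
| 50 | 5 | 0/45 = 0.0% | 5/50 = 10.0% |
| 100 | 5 | 0/95 = 0.0% | 5/100 = 5.0% |

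The last row treats the 100 PHD or follow-up cases as 100 patients and assumes that the PHD/follow-up set has been formed as intended.

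**What is not affected.** Footnote 23 applies the same condition to events and assigns no misnamed variable. A patient has `n ade dd SAR` of at least 1 exactly when the composite flag should be Yes, so the correct proportion can be recovered from the count. The listings of adjudicated AEs and DDs in SAP 10.2 do not use the flag at all.

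**Other names that do not match.**
- *Footnotes 4 and 8.* The table in SAP 7.1 declares `analysis set PHD FUP SAR`, and footnotes 12, 24, 27 and 61 select on it. Footnote 4 assigns both Yes and No to `analysis set FUP SAR`, and footnote 8 selects on that shorter name.
- *Footnote 13.* The table in SAP 8.5 declares `FU renamicneo SAR` for use of the programmer at follow-up, but the footnote assigns both branches to `PHD renamicneo SAR`, the variable already derived in footnote 11.

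**The case against.** The strongest reply is that this is a slip of the pen in a footnote written for people. The label, the condition, the ELSE branch and the pattern of footnotes 16 to 18 allow only one reading, and a competent programmer would use it. That stands as to intent. It does not remove the need to correct the text: SAP 1.1 presents the document as detailed instructions, and CIP 11.8 requires any departure from the valid SAP to be indicated in the statistical and clinical reports, so a silent repair would itself be an undeclared deviation.

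The second reply is that little hangs on the flag. CIP 7.2.2 defines the endpoint as a number of events per number of cases, which corresponds to `n ade dd SAR`. There is no hypothesis (CIP 7.2.1) and no pass/fail criterion (CIP 11.5), and every ADE or DD is to be discussed. The standard table in SAP 5.1 also prints N total beside N non-missing, so 50 against 47 would show. All of this stands and sets the severity.

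A reader might infer that the study endpoint itself is lost. The documents do not support that, because the count and the listings survive. A reader might also infer that footnote 4 has the same fault and that the PHD/follow-up chapters would select nobody. Footnote 4 differs in kind: both of its branches use one name, footnote 8 uses it too, and the footnote number ties it to the declared variable. It is a consistent alias that needs harmonising. Nor could both literal consequences occur together, since an empty chapter 11 would contain no percentage to distort.

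**Conclusion.** Footnote 19 is wrong as written. Executed literally, the per-patient composite flag is never Yes, patients with an event become missing, and the reported percentage is 0% regardless of the data; with an assumed 3 of 50 that is 0/47 in place of 6.0%. SAP 11.1 carries the rule into the PHD/follow-up chapter. The size depends on literal programming and on at least one relevant event occurring; with no events, the written and intended rules agree (0/50).

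Severity is minor to moderate. The most likely harm is an internally inconsistent report, with a 0% composite beside non-zero counts and listings, and not concealed events. No sample-size or probability figure changes. The mismatches in footnotes 4, 8 and 13 are separate naming matters.

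**What to change.** In footnote 19, write the THEN branch to `any ade dd SAR`, leaving the condition and the ELSE branch as they are.

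As separate harmonisation:
- use `analysis set PHD FUP SAR` in both branches of footnote 4 and in footnote 8;
- use `FU renamicneo SAR` in both branches of footnote 13.

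That is six small edits: one in footnote 19, two in footnote 4, one in footnote 8 and two in footnote 13. A useful program check is that `any ade dd SAR` is Yes exactly when `n ade dd SAR` is at least 1, and that it has no missing values within the analysis set.

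CIP 11.8 allows the SAP to be updated before database freeze or closure, so the change can go into the next version with a line in the change history. It needs no new data and does not alter the design. If an interim output has already been produced from these footnotes, the composite row should be checked against the counts.
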